## 5. Hypothesis

- 1. Initiation of persistent beta-cell autoimmunity and progression from beta-cell autoimmunity to diabetes is increased with:
  - a. Exposure to a trigger factor during pregnancy, such as infections, preeclampsia, blood incompatibility, or birth weight.
  - b. Differences in the timing of the introduction and/or the type of dietary constituents that include exposure to cereals or gluten, exposure to cow's milk during infancy and/or childhood, and short duration of breast-feeding;
  - c. Lower intake of serum 25 hydroxyvitamin D in early infancy, vitamin E, antioxidants (e.g., carotenoids, ascorbic acid, selenium, or omega-3 fatty acids);
  - d. Higher frequency of specific (e.g., enterovirus, rotavirus, or bacterial) infections, or non-specific childhood infections including those that exhibit molecular mimicry;
  - e. Increased exposure to routine childhood immunizations and their timing;
  - f. Environmental factors that may be contained in drinking water (e.g., low concentrations of zinc or high concentrations of nitrates, or lower pH levels);
  - g. Exposure to household pets, and various allergies;
  - h. Excessive weight gain;
  - i. Increased psychological stress.
- 2. The risk of persistent beta-cell autoimmunity is lower in children from the general population than in offspring or siblings of T1DM patients when stratifying for the HLA DR-DQ genotype and exposure to environmental triggers.
- 3. The interaction of HLA DR-DQ genotype with exposure to dietary or infectious factors leads to increased incidence of beta-cell autoimmunity and T1DM.

4. We expect that in some families study participation will be associated with affective (anxiety, depression) and behavioral responses (e.g. actions to prevent possible T1DM).

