## 8.14.6.1. Background

The goals of the dietary collection component of TEDDY are 1) to identify dietary factors that predispose to or protect from islet autoimmunity and T1DM; and 2) to identify potential differences in dietary determinants of islet autoimmunity and T1DM across diverse populations and ethnic groups. TEDDY is designed to test and confirm existing dietary hypotheses as well as explore new, less well-documented hypotheses. Examples of the former include: initiation of persistent islet autoimmunity is associated with 1) early and late exposure to cereals or gluten in the infant diet and/or short duration of breast-feeding; 2) exposure to cow milk in infancy and later in childhood; and 3) lower intake of vitamin D or omega-3 fatty acids, an example of the latter is the collection of maternal diet during pregnancy. Studies from DAISY and BABYDIAB investigators recently suggested a strong association between timing of first exposure to cereals and risk of islet autoimmunity ([name] et al, 2003; [name] et al, 2003). These two studies, while remarkably consistent, did not agree on whether the exposure in question was to all cereals or to only gluten-containing cereals; and whether late first exposure (after 6 months) increased risk of islet autoimmunity in addition to early exposure. In order to investigate this issue further and resolve these discrepancies across studies, it is necessary to use common data collection protocols, the same recruitment criteria and the same follow-up protocols. Questions remain as to whether this association is driven by dose or quantity of exposure, or whether it is related to a proportional measure, such as percent energy from carbohydrates. In order to quantify exposure, one needs to collect information on the entire diet, which would allow one to get absolute intake (as opposed to frequency) and to adjust for energy intake. This requires the collection of a food record. There are no adequate biomarkers to measure the intake of cereals or specifically gluten. The findings of both case-control and cohort studies are inconsistent regarding the putative effects of cow milk intake on beta-cell autoimmunity and type 1 diabetes (reviewed in Virtanen and Knip 2003).

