## 10.1. Master Plan of Analysis

The primary goal of the statistical analyses to be performed as part of this study will be the identification of factors associated with the development of autoimmunity and T1DM. In order to accomplish this, we will employ two different types of analysis, depending on the nature of the factor being studied.

- For those factors whose values will be known to us without additional costs, we will perform log rank tests and Cox Proportional Hazards Regressions. For these analyses, the dependent variable will be the age at which the event being studied (development of autoimmunity or diagnosis of T1DM) occurred. Those not achieving the event when the analyses are being performed and those lost to follow-up without achieving the event will be considered censored as of the date last known to be event-free. The log rank test will be used to study factors with a few discrete values. For example:
  - (a) Family History
  - (b) Haplotype
  - (c) Breast-feeding

For factors with continuous values, we will test for conformity of those values with the proportional hazards assumption by examining the significance of the interaction of the time variable (treated as a time-dependent covariate) with the factor. If there is an indication of a non-zero interaction coefficient, (p < 0.10) we will dichotomize the variable and use the log rank test instead of proportional hazards regression. Otherwise, we will use proportional hazards regression to test for significance at the .01 significance level. The following are examples of factors to be studied in this manner:

- (a) Amounts of certain nutrients consumed
- (b) Duration of breast feeding
- (c) Maternal anxiety and depression as measured by the State Trait Anxiety Inventory and the Edinburgh Postnatal Depression Scale

Proportional hazards regression will be used in both a univariate and multivariate manner and reported both ways. For each factor studied, estimated hazard ratios and their 95% confidence intervals will be computed. When a set of factors that predict conversion to T1DM or autoimmunity are determined as described above, we will compute estimated "survival" curves for subjects having specific factor profiles.

2) For those factors whose determination is costly we will employ a nested casecontrol design. At the time at which a cohort subject converts to autoimmunity or

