The following is a non-exhaustive listing of planned statistical analyses for the prospective part of the project:

- 1. We will classify infants as to whether or not they had early exposure to cereals or gluten in the diet (vs. those receiving only breast milk for the first 3 months). Those exposed will be compared to those not exposed using the Log Rank Test.
- Subjects will be classified, based on diet questionnaires, as consuming low or high levels of anti-oxidants such as carotenoids, ascorbic acid, and selenium. Those with low levels will be compared to those with high levels with respect to the development of T1DM and autoimmunity using Log Rank Tests.

- 3. Subjects' drinking water will be analyzed and subjects classified as drinking water with high or low concentrations of zinc, and nitrate and as low or high pH. Groups will be compared using the Log Rank Test.
- 4. Cox Regression will be used to study the association of the level of psychosocial stress with the development of T1DM and autoimmunity.

The following analyses will be performed in the nested case control portion of the study:

- The association between the number of enterovirus infections a child has and the development of T1DM and islet autoimmunity will be studied with Cox Regression. Using zero as the reference, dummy variables will be created to represent 1, 2, etc infections. The hazard ratios of these values relative to zero will be estimated and p values of the estimates computed. The same type of analyses will be done for the number of rotavirus infections.
- 2. Low levels of omega-3 fatty acids, EPA, and DHA in children's erythrocyte membranes have been associated with increased risk of islet autoimmunity. The odds ratio for each of these exposures will be estimated.
- 3. Low levels of alpha-tocopherol has been associated with increased risk of islet autoimmunity. The odds ratio for each of this exposure will be estimated

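### The first listed prospective analysis compares early cereal or gluten with a breast-milk-only reference in an unadjusted log rank test, so cereal timing is confounded with milk feeding

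*Protocol*

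**What the plan says.** Section 10.1 introduces its list with "The following is a non-exhaustive listing of planned statistical analyses for the prospective part of the project". Item 1 divides infants by "early exposure to cereals or gluten in the diet (vs. those receiving only breast milk for the first 3 months", and continues: "Those exposed will be compared to those not exposed using the Log Rank Test". No stratification or adjustment is mentioned in the item.

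Other parts of the protocol bear on this contrast:

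- **Section 5, hypothesis 1b** begins "Differences in the timing of the introduction and/or the type of dietary constituents that include exposure to cereals or gluten", then names cow's milk exposure and "short duration of breast-feeding" as further exposures.
- **Section 8.14.6.1** says that two earlier cohort studies disagreed on whether all cereals or only gluten-containing cereals matter, and on "whether late first exposure (after 6 months) increased risk of islet autoimmunity in addition to early exposure". It includes both early and late cereal or gluten exposure among its example hypotheses.
- **Section 10.1, master plan**, says "Proportional hazards regression will be used in both a univariate and multivariate manner and reported both ways". It gives breast-feeding as a discrete log rank factor and "Duration of breast feeding" as a continuous one. It does not say which covariates enter the multivariate models.
- **Section 8.12.1.2** provides for recording total and exclusive breast-feeding duration, the formulas used, and when foods were introduced during the first two years.
- **Section 10.2.3** gives gluten foods before 3 months and cereals at 0 to 3 months as two separate interim examples, without a breast-milk-only reference.

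**The concern.** A comparison meant to isolate cereal timing should leave other feeding the same, or adjust for it. Item 1 does neither. Its bracketed reference has had no early cereal and no formula, while the exposed group may contain both breast-fed and formula-fed infants. Two exposures that the protocol hypothesises separately, and expects to act in the same direction, change together.

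The item is also open to two constructions. Its main wording splits infants into exposed and not exposed; its bracket restricts the unexposed to infants fed only breast milk. Two analysts could build different datasets from the same sentence.

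Finally, the item joins cereals with gluten and makes a single cut at 3 months. Within this analysis it therefore cannot distinguish gluten from other cereals, and children first exposed after 6 months sit in the reference beside those introduced between 3 and 6 months. A positive result from the first listed prospective analysis could be misattributed, and a late-introduction effect would go unseen in it.

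**Working it through.** **Step 1. Where each feeding group falls (first 3 months)**

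| Feeding | Bracket taken literally | Exposed/not-exposed wording |
|---|---|---|
| Cereal, breast-fed | exposed | exposed |
| Cereal, formula-fed | exposed | exposed |
| No cereal, breast milk only | reference | reference |
| No cereal, formula-fed | neither | reference |

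The readings differ in the last row. Under the bracket, no reference infant is formula-fed.

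**Step 2. The protocol's nearest figures**

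Item 1 states no number. The nearest are the log rank powers at HR 1.5, 10% exposed and no loss to follow-up: 0.52 for T1DM (Table 6) and 0.93 for autoantibodies (Table 9). Inputs are N = 7,013, two-sided alpha 0.01, and 4% conversion among the unexposed at 15 and 6 years respectively. The exponential hazards are −ln(0.96)/15 = 0.00272 and −ln(0.96)/6 = 0.00680 per year. A Lakatos-type calculation with 5 years' uniform accrual plus 15 further years returns 0.52 and 0.93, and all 26 Table 6 cells checked agree within 2 points. With exactly 15 years per child the T1DM cell would be about 0.45, so the longer follow-up is used below to match the tables.

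**Step 3. Apparent cereal effect when there is none**

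For a rare outcome, apparent HR = 1 + q × (HR of formula − 1), where q is the excess share of formula-fed infants in the exposed group. The protocol gives neither quantity; both are assumptions. The last two columns give the chance of p < 0.01 at 10% exposed, no loss and full N, against a nominal 0.01.

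| Formula HR | q | Apparent HR | T1DM | Autoantibodies |
|---|---|---|---|---|
| 1.25 | 0.5 | 1 + 0.5 × 0.25 = 1.125 | 0.03 | 0.06 |
| 1.5 | 0.5 | 1 + 0.5 × 0.5 = 1.25 | 0.11 | 0.30 |
| 1.5 | 1.0 | 1 + 1.0 × 0.5 = 1.50 | 0.52 | 0.93 |
| 2.0 | 1.0 | 1 + 1.0 × 1.0 = 2.00 | 0.99 | 1.00 |

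If formula-fed infants without cereal stay in the reference, the bias shrinks but need not vanish. With formula HR 1.5, all exposed and half of the reference formula-fed, the apparent HR is (1 + 1.0 × 0.5)/(1 + 0.5 × 0.5) = 1.50/1.25 = 1.20.

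**Step 4. Sample lost under the literal bracket**

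With 10% exposed there are 701 exposed and 6,312 unexposed infants. If breast-milk-only infants are an assumed 20%, 40% or 60% of the unexposed, N is 1,964, 3,226 or 4,488. Power at HR 1.5 becomes 0.32, 0.43 or 0.48 for T1DM and 0.75, 0.87 or 0.90 for autoantibodies. The detection chances in step 3 would fall accordingly; the bias in the estimate would not.

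**Step 5. Late introducers inside the reference**

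If a share s of the reference is introduced late with hazard ratio h, the observed early HR is the true HR divided by (1 − s + s × h). With s = 0.30 and h = 2, a true early HR of 2.0 is seen as 2.0/(0.70 + 0.60) = 1.54. With s = 0.15, a true HR of 4.0 is seen as 4.0/(0.85 + 0.30) = 3.5. Both s and h are assumptions.

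**The case against.** The best reply is that item 1 is one example in an open list and the plan around it is wider. Multivariate Cox models are to be reported, breast-feeding is analysed in its own right, and the data needed for a better contrast are collected. Covariate sets and cut-points are often left to a SAP, which is not at hand. Much of this stands, and it rules out three stronger readings that a reader might infer:

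- **That a milk-feeding effect will be reported as a cereal effect.** This requires such an effect to exist. Sections 2 and 8.14.6.1 call the earlier findings on breast-feeding and cow's milk inconsistent, and adjusted models are planned.
- **That adjustment could not separate cereal from milk.** Even under the literal bracket, breast-fed infants given cereal can be compared with both other cells. A main-effects model then estimates both effects, assuming no interaction, unless every early-cereal infant is formula-fed. Models on the whole cohort can also use formula-fed infants without cereal.
- **That the study cannot answer the late-introduction question.** Only item 1 cannot. Section 8.14.6.1 does not assign that question to this test, and further analyses are allowed.

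It is also fair that the exposed/not-exposed wording can be read as keeping formula-fed infants without cereal in the reference; their exclusion is one reading.

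The reply does not repair the listed contrast. The Cox sentence names no covariates, item 1 names the log rank test while item 4 of the same list names Cox, and a separate breast-feeding test does not remove confounding from this one. An open list permits other analyses; it does not correct one that is stated.

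**Conclusion.** The point holds for item 1 as written. It is a stated rule, not missing detail: an unadjusted test of a contrast in which cereal and milk feeding change together, with a reference group worded in two incompatible ways. It also merges the gluten/all-cereal and middle/late distinctions that Section 8.14.6.1 describes as unresolved.

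The size is conditional. With no cereal effect, a formula HR of 1.5 and an excess formula share of 0.5 to 1.0, the apparent HR is 1.25 to 1.50. At 10% exposed with no loss and full N, the chance of a nominally significant result is then 0.11 to 0.52 for T1DM and 0.30 to 0.93 for autoantibodies. With a formula HR of 1.25 and a share of 0.5 it is only 0.03 and 0.06, and with no milk-feeding effect this source of bias disappears. None of the assumed feeding effects or shares comes from the protocol.

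**What to change.** Reword item 1 of the prospective list in Section 10.1:

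1. Delete the breast-milk-only bracket.
2. Define groups by age at first cereal regardless of milk feeding, using the cut-points the protocol already uses: by 3 months, between 3 and 6 months, and after 6 months, with the middle group as reference. State on which side the boundary ages fall.
3. Repeat the classification separately for first gluten.
4. Stratify the log rank test, or adjust the Cox model, for breast-feeding and formula status at 3 months, and name that covariate in the item.

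This places formula-fed infants without early cereal by their cereal age and lets the item address both questions from Section 8.14.6.1. It needs no new data, since Section 8.12.1.2 already covers the feeding history. The cost is a wording change, slightly more analysis work and one more exposure category.

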Demographic/Family History/Other questionnaire											Х									Demograph		e updated eve be updated ev			nily History		
TEDDY Book Extraction					X			x			X			X	x	X	x	x	X		X#			X #			
Child Behavior Checklist/ Strengths and Difficulties Questionnaire																					CBCL completed when child is 3.5, 4.5 and 5.5 years of age; SDQ completed by both parent and child when child is 11.5 and 13.5 years of age						
Physical Activity Assessment																									X (begins at 5 years)%		
Pubertal Status Assessment																								X (begins at 8 years)			

\*If cord blood is not available at birth for HLA typing then capillary blood should be drawn.

+ If venous blood is not available at every three month office visit, then capillary blood should be taken.

\*\* A blood sample will be obtained by the 24 month visit from mothers who have type 1 or 2 diabetes or gestational diabetes as well as from a mother whose child is shown to be autoantibody positive at three or six months of age. An optional venous blood draw of the mother is obtained at 12-14 weeks of pregnancy, and at the birth of the baby.

#Children four years of age and older who have been deemed persistent autoantibody positive will remain on the three month visit schedule; this sample/form will be collected/completed at these visits.

^ Continue to collect 3 day diet records every 6 months from subjects who are single or multiple persistent confirmed autoantibody positive (even if the subject reverts to autoantibody negativity), stop 3 day diet record collections on all other subjects after the 10 year visit. Should a subject be deemed single or multiple persistent confirmed autoantibody positive after the 10 year visit, the 3 day diet record collection will be restarted at the next visit.

% Continue to collect physical activity assessments annually from subjects who are single or multiple persistent confirmed autoantibody positive (even if the subject reverts to autoantibody negativity), stop physical activity assessments on all other subjects after the 10 year visit. Should a subject be deemed single or multiple persistent confirmed autoantibody positive after the 10 year visit, the physical activity assessment will be restarted at the next visit.

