## 8.12.1.2. Dietary study in children

In addition to food consumption, dietary habits of the participating infants (e.g. feeding pattern) will be assessed by mailed questionnaire that is to be completed prior to the first clinic visit, a structured interview at each clinic

visit, and records kept by the mother in the TEDDY Book (see Table 2 and section 8.11.2). The duration of total and exclusive breastfeeding, age at introduction of various foods during the first 2 years of life, type of infant formulas used, source of drinking water (local waterworks, bottled water, private wells), elimination diets, and use of dietary supplements will be recorded.

Primary caretakers (usually mothers) will be trained during the three-month clinic visit to keep 3-day food diaries of the child's dietary intake at 3 month intervals during the first year of life and biannually thereafter. A 24-hour recall of the child's diet will be obtained at the first (3-month) visit. The collection of this 24-hour recall will have two purposes: 1) to assist in *training* the primary caretakers in what types of food items they will need to record when they complete the 3-day diet records; and 2) the dietary data from the 24-hour recall will be used to reflect the infant's diet at 3 months of age. The first 3-day food diary will be given to the primary caretaker at the threemonth visit after training. The primary caretaker will be instructed to fill out the 3-day food diary directly prior to the next clinic visit (in this case the 6 month clinic visit), so that they can bring the completed record with them (Gregory et al., 1995). At each clinic visit, the diet records will be reviewed by trained study personnel with the primary caretaker.

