In August 2018, the collection protocol was changed so as to continue to collect 3 day diet records every 6 months from subjects who are single or multiple persistent confirmed autoantibody positive (even if the subject reverts to autoantibody negativity) and to stop 3 day diet record collections on all other subjects after the 10 year visit. Should a subject be deemed single or multiple persistent confirmed autoantibody positive after the 10 year visit, the 3 day diet record collection will be restarted at the next visit. This will provide a complete dataset on all subjects up through 10 years of age and continued collection on persistent confirmed autoantibody positive subjects through the end of the study. Continued data collection on persistent confirmed autoantibody positive individuals will enable the TEDDY study to explore the role of diet, and dietary changes, through early adolescent years, on progression to T1D. It has been noted that the diet of individuals in this 10-15 year age interval is changed as compared to the diet at younger ages. These data will enable TEDDY to include these dietary patterns in assessments of T1D risk along with other exposures and changes occurring during the peripubertal period to include energy intake, energy expenditure, growth, hormonal changes and glucose demand. Epidemiological data points to increased T1D incidence during this period, TEDDY has also observed a declining rate of conversion from autoantibody negative to autoantibody positive (i.e., lower incidence of seroconversion during this age range). This reduces the statistical power to see an effect of dietary changes during the 10-15 year age range. Coupled with a lower compliance rate, as compared to families completing the 3 day diet record whose child is persistent confirmed

autoantibody positive, it seems prudent to reduce the burden on families and clinic staff by discontinuing data collection after 10 years of age for families whose child is autoantibody negative. TEDDY will have a complete data set on this population through age 10 years so it will be able to address the contribution of diet in the cumulative incidence of islet cell autoimmunity up to this age.

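### Section 10.1 compares fixed low and high antioxidant-intake groups by log-rank on age at event, but intake is recorded after birth for a length of time that depends on outcome, so the groups can show a false association in either direction

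*Protocol*

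**What the plan says.** All references are to the protocol; no SAP is at hand.

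- **Grouping and test (10.1, prospective item 2).** "Subjects will be classified, based on diet questionnaires, as consuming low or high levels of anti-oxidants such as carotenoids, ascorbic acid, and selenium". Then: "Those with low levels will be compared to those with high levels with respect to the development of T1DM and autoimmunity using Log Rank Tests". No age window, landmark or last usable record is given.
- **Time axis (10.1).** "the dependent variable will be the age at which the event being studied (development of autoimmunity or diagnosis of T1DM) occurred". Follow-up therefore runs from birth, and no delayed entry is stated.
- **Continuous route (10.1).** "Amounts of certain nutrients consumed" is listed as a factor for Cox regression. If the proportional-hazards check gives p < 0.10, the factor is dichotomised and returned to the log-rank test.
- **When intake is recorded (8.12.1.2).** A 24-hour recall at 3 months, then "3-day food diaries of the child's dietary intake at 3 month intervals during the first year of life and biannually thereafter".
- **After age 10 (8.12.1.2).** The August 2018 change was "to stop 3 day diet record collections on all other subjects after the 10 year visit". The footnote to Table 2 adds: "Continue to collect 3 day diet records every 6 months from subjects who are single or multiple persistent confirmed autoantibody positive".
- **Elsewhere.** Time-dependent exposure covariates appear only in 10.6, under gene-environment interactions. Section 8.14.6.1 says full diet records permit energy adjustment.

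**The concern.** A log-rank test treats group membership as fixed at time zero. Here membership is decided by information that arrives later, and the amount of information depends on the outcome. Two mechanisms follow.

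1. If records are used up to the event, a child with an event at age 2 is grouped on toddler intake, while a child event-free at 10 is grouped on ten years of intake. If absolute intake grows with age, the first child drifts towards the low group with no difference in dietary habit.
2. If all available records are used, converters contribute records after conversion, and after age 10 they are the ones who continue. They then drift towards the high group.

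The first mechanism would yield a result in the direction of hypothesis 1c (Section 5: lower antioxidant intake raises risk). The second could hide or reverse a real effect. Other parts of the plan avoid the problem. Item 1 of the same list limits its exposure to the first 3 months, and the nested case-control arm matches on duration of follow-up.

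**Working it through.** **The plan's own figures.** The protocol gives no figure for the low/high nutrient comparison. The nearest are the log-rank power tables in 10.3. Lakatos-type noncentrality:

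φ = Σdᵢ[rᵢθ/(1+rᵢθ) − rᵢ/(1+rᵢ)] / √(Σdᵢrᵢ/(1+rᵢ)²), power = Φ(|φ| − 2.576)

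Here r is the exposed:unexposed at-risk ratio and θ the hazard ratio, with 5 years of accrual plus 15 years and two-sided alpha 0.01. Table 9 (10% exposed, HR 1.5, no loss) gives 0.931 against 0.93 stated. Table 6 gives 0.522 against 0.52 (10% exposed) and 0.803 against 0.81 (20% exposed). These figures are not in dispute, but 10.3 computes them for triggers fixed before birth, which childhood intake is not.

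**Size of the drift by hand.** Assume intake rises linearly from 1 at age 1 to F at age 10: I(a) = 1 + (F−1)(a−1)/9. Diaries fall at 6, 9 and 12 months, then every 6 months.

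- Event at age 2: ages 0.5, 0.75, 1, 1.5, 2; mean age 5.75/5 = 1.15.
- Event-free to 10: 21 records; mean age (2.25 + 103.5)/21 = 5.04.
- F = 2: (1 + 0.15/9)/(1 + 4.04/9) = 1.017/1.449 = 0.70.
- F = 1.5: 1.008/1.224 = 0.82.
- F = 1.25: 1.004/1.112 = 0.90.

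The same eating pattern therefore yields a recorded mean 10% to 30% lower merely because follow-up was shorter.

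**Null simulation (true HR 1).** From the protocol: N = 7,013; 4% T1DM by 15, hazard −ln(0.96)/15 = 0.0027 per year; 4% autoimmunity by 6, hazard −ln(0.96)/6 = 0.0068 per year; 2% loss per year; the diary schedule; alpha 0.01. Assumed: log-normal intake with between- and within-child SD 0.35 on the log scale, a median split, and the age trend.

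*Rule A: unadjusted mean of records up to the event or age 10.* Where runs were repeated, the range is shown.

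| Rise, age 1 to 10 | Low-vs-high HR, T1DM | Rejection, T1DM | Rejection, autoimmunity |
|---|---|---|---|
| flat | 1.02 | 1% | 2.5% |
| 1.25-fold | 1.21 | 9–15% | 40–41% |
| 1.5-fold | 1.39–1.42 | 47–48% | 90–92% |
| 2-fold | 1.73–1.76 | 94–96% | 100% |

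*Rule B: post-conversion records included, autoimmunity, same three rises.*

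- All records to age 10 for everyone: HR 1.00, 1.01, 0.99; rejection 0–1%.
- Records on the schedule in Table 2 and 8.12.1.2: HR 0.78, 0.67, 0.52. A separate set of runs ranged from 0.78 to 0.46.
- T1DM on that schedule: HR 1.19, 1.32, 1.62. It does not reverse, because participation ends shortly after diagnosis (9.2.1).

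**Other assumptions.** Pooled sample of 7,801, 5.5% autoimmunity by 6, both SDs 0.5, 400 runs, loss 0% or 5% per year. High-vs-low results are inverted here to low-vs-high.

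- Mean to exit, mild rise: 1/0.75 = 1.33. Strong rise: 1/0.53 = 1.89 and 1/0.50 = 2.00.
- Mean to exit, mild fall: 1/1.23 = 0.81, so the direction reverses.
- Cumulative intake to exit: 1/0.41 = 2.4 to 1/0.23 = 4.3 across all trends, including flat and falling.

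**After correction.** In the same 400-run setting:

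- First-year intake with a landmark at age 1: HR 1.00 to 1.01, rejection 0.5–2.0%.
- Time-dependent running mean: HR 1.00 to 1.01, rejection 0.3–1.5%.
- Age-standardised mean: HR 1.00 to 1.01, rejection 0.3–2.0%.

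First-year intake analysed from birth gives a high-vs-low HR of 0.98 to 1.00.

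**The case against.** The best reply is that the exposure rule simulated under Rule A is not in the protocol. Item 2 names no averaging rule or window, the list of analyses is described as non-exhaustive, and deriving an exposure variable is ordinary SAP work. Section 8.14.6.1 foresees energy adjustment, which could remove much of an age trend, and the protocol gives no trend for these nutrients. Carotenoids and ascorbic acid are also measured in plasma and selenium in toenails. Biomarkers go to case-control sets matched on duration of follow-up, so a dietary artefact would face an independent check. Section 10.2.3 promises caution in interpretation.

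Much of this stands, and it rules out two stronger readings.

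- A reader might infer that early converters will be classed low and that false protection will appear on both endpoints. The documents do not support that. Converters stay in follow-up and keep supplying diet records, and depending on which records are used the autoimmunity result is biased upwards, unbiased or reversed.
- A reader might also infer that the log-rank test must go. It need not: groups from first-year intake are almost unbiased even when analysed from birth.

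What does not stand is the claim that this is only missing detail. The protocol itself fixes one group per child, the test and the time axis. Combined with records whose extent depends on outcome, those choices permit badly biased analyses. The Cox route does not protect against this either, since a fixed amount has the same fault and can be sent back to the log-rank test.

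**Conclusion.** The point holds in conditional form. As written, item 2 allows a group that depends on event-free time or case status to be analysed as if known at birth.

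- **Unadjusted mean intake to the event, rising 1.25- to 2-fold from age 1 to 10:** null low-vs-high HR about 1.2 to 1.75. The upper part falls within the 1.5 to 2.0 range for which the study is powered, and the direction matches hypothesis 1c.
- **Post-conversion records on the collection schedule:** the direction reverses for autoimmunity.
- **Flat or age-standardised intake:** negligible bias.

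The sizes rest on the assumed age trend, the assumed SDs, constant hazards and a median split. The reversed figures also assume that diaries stop at age 10 in every non-converter. The stop dates from August 2018, and recruitment ran from 2004 to 2009, so the oldest children had already passed 10. The true imbalance would be smaller. The rejection percentages for autoimmunity apply only if records are cut at conversion, which the protocol does not say. The point is worth settling before these analyses are run, but it does not affect the study's data or its power tables.

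**What to change.** Amend 10.1 for nutrient intake in one of two ways.

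1. Analyse intake as a time-dependent covariate in the age-scale Cox model, using at each event age only records made before it, standardised for age at record and energy-adjusted.
2. Keep the log-rank test, but define low and high from a fixed early window (for example, records to 12 months), start follow-up at the end of that window, and exclude post-event records.

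Apply the same rule to the continuous nutrient amounts, including when a failed proportional-hazards check leads to dichotomisation.

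The cost is wording and programming; no new data are needed. A landmark leaves out events before it, and an early window says nothing about later intake. If later intake matters, the first option is the better choice.
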